Visit number	Admit		Treatment period									Follow-up		
	1		2	3	4	5	6	7	8	9	10	11 EOS		
Study week (beginning of week except Day 140)				1	2	3	4	5	9	13	17	20	23	25
Procedure (Study Day)	Admit Day -2	Day -1 ^b	Day 1 ^b	Day 2 ^b	Day 8	Day 15	Day 22	Day 29	Day 57	Day 85	Day 113	Day 140 ^m	Day 155	Day 169
Overnight Residency	X ^a	X ^a	X ^a											
Informed Consent	X													
Review Inclusion/Exclusion Criteria	X	X												
Medication and Medical History	X ^c													
Weight/BMI & Temperature	X	X	X	X		X		X		X		X	X	X
Orthostatic Standing Test including supine blood pressure ^d		X ^d	X ^d	X ^d		X ^d		X ^d		X ^d		X ^d	X ^d	X ^d
Supine blood pressure ^e	X ^e				X ^e		X ^e		X ^e		X ^e			
24 hour blood pressure monitoring ^f		X ^f				X ^f		X ^f		X ^f				X ^f
ECG (12-lead)		X												X
Physical Examination ^g		X ^g	X ^g	X ^g		X ^g		X ^g		X ^g		X ^g	X ^g	X ^g
Urine Pregnancy Test ^h	X ^h													
Safety labs: Hematology, Chemistry, and UA	X ^o													X
PK Sampling ⁱ			X ⁱ	X ⁱ		X ⁱ		X ⁱ		X ⁱ		X ⁱ		X ⁱ
DHPG Sampling ^j			X ^j	X ^j				X ^j						
NE Sampling ^k			X ^k					X ^k						
OHQ (OHSA and OHDAS) ^l		X ^l	X ^l	X ^l	X ^l	X ^l	X ^l	X ^l	X ^l	X ^l	X ^l	X ^l	X ^l	
Clinician's/Subject's Global Impression ^l		X ^l	X ^l	X ^l	X ^l	X ^l	X ^l	X ^l	X ^l	X ^l	X ^l	X ^l	X ^l	
Concomitant Medications	X	X	X	X	X	X	X	X	X	X	X	X	X	X
Adverse Events	X	X	X	X	X	X	X	X	X	X	X	X	X	X
Study Drug Administration ^m			X ^m	X ^m	X ^m	X ^m	X ^m	X ^m	X ^m	X ^m	X ^m	X ^m	X ^m	
Subject Satisfaction Survey ⁿ			X ⁿ			X ⁿ		X ⁿ				X ⁿ		
Telephone Assessments (highlighted in gray)					X		X		X		X			

SCHEDULE OF STUDY ASSESSMENTS (CONTINUED)

- a. Subjects will admit to the research unit on Day -2 and remain resident through the completion of study procedures on the morning of Day 2.
- b. The timing of Day -1 "postdose" assessments should be prospectively calculated, based on the target Day 1 dosing time (eg, orthostatic standing test and Clinical Impression and OHQ assessments). Study Day 1 is defined as the day of first study dosing with TD-9855 in Part C. On Day 2 subjects are discharged from the research facility after all study procedures are completed the morning of Day 2.
- c. History update, if any changes since participation in Part A (and B if appropriate) of the study.

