- k. Blood collection for NE analysis will be collected on Day 1 (within 30 minutes before dosing) and upon return to the clinic on Day 29. Please refer to the central laboratory manual.

SCHEDULE OF STUDY ASSESSMENTS (CONTINUED)

- I. Clinician's/Subject's Global Impression and OHQ (OHSA and OHDAS components) to be administered during clinic visits by a trained clinician and recorded on standardized paper forms (See [Appendix 4](#)). In addition while at home, the Clinician's/Subject's Global Impression and OHQ will be completed by telephone with the study coordinator. On all visit days the OHQ and Global Impression assessments should be completed at least 4 hours after dosing (but no more than 7 hours) and before lunch. For the Day 155 and 169 assessments, the timing of the "postdose" questionnaires should be calculated based on the Day 1 dosing time.
- m. On the study visit days marked above, subjects will receive a dose of study medication in the morning after supine blood pressures and the orthostatic standing test has been completed. On non-study visit days the subjects should take their dose of study medication in the morning at approximately the same time of day. On study days where the subject is traveling to the clinic, the subject should take their dose of study medication at home before traveling to the clinic. Subjects will return to the clinic on the day of their final dose. Day 140 is the day of the last dose received at the end of 5 months (20 weeks).
- n. Subjects will complete the Subject Satisfaction Survey on Days -1, 15, 29 and 140 (or at the time of early discontinuation) using the appropriate questionnaire listed in [Appendix 5](#).
- o. Safety labs should be collected Day -2 or on Day -1.

Sequence of study procedures during study visits (with *hypothetical* times for illustration):

- 7:00 am -Wake up
- 7:30 am - supine blood pressure after 5 and 10 minutes resting at 30 degrees elevation and orthostatic standing test (where applicable)
- 8:00 am - Dose with TD-9855 and eat breakfast

After a minimum of 4 hours but no more than 7 hours after dosing and before lunch:

- 12:00 pm - supine blood pressure after 5 and 10 minutes resting at 30 degrees elevation and orthostatic standing test (where applicable)
- 12:30 pm - Clinician/subject impression and OH Questionnaires (OHDAS and OHSA)
- 12:45 pm - lunch

TABLE OF CONTENTS

	PAGE
PROTOCOL SYNOPSIS	2
SCHEDULE OF STUDY ASSESSMENTS	12
LIST OF ABBREVIATIONS AND DEFINITION OF TERMS	20

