6.2 Total Blood Volume

The total volume of blood to be drawn from each subject for safety, PK, and PD laboratory assessments is approximately [REDACTED]

Additional safety laboratory tests may be drawn as needed to manage any emergent health needs as directed by the Investigator.

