6 GENERAL ANALYSIS CONSIDERATIONS

6.1 Global Definitions and Conventions

All data from scheduled and unscheduled visits will be presented in the subject listings; however, unless noted otherwise, only data from scheduled visits will be included in the summaries, statistical analysis, and calculation of derived parameters.

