6.3 Analysis Windows

All assessments will be summarized using analysis windows. The terminology of unscheduled will be applied to assessments that are outside an analysis window regardless, of the nominal label associated with the assessments in the EDC system.

All data (scheduled and unscheduled visits) will be presented in the subject listings; however, unless noted otherwise, only data from assessments within analysis windows will be included in the summaries, statistical analysis, and calculation of derived parameters.

In part C, the analysis window will be +/-3 days for the scheduled visits from Day 8 through Day 29, ±7 days for scheduled visits between Day 57 through Day 169 as defined below.

Nominal Day	Start (days)	Stop (days)
8	5	11
15	12	18

Nominal Day	Start (days)	Stop (days)
22	19	25
29	26	32
57	50	64
85	78	92
113	106	120
140	133	147
155	148	162
169	163	175

If the scheduled visit is outside of the analysis window, data will not be counted in the summary tables. In each part, the summary tables by the scheduled visit will only use data recorded for the scheduled visit. Data collected at the unscheduled visit will not be counted in the summary table, however will be included in the subject listings.

General Selection Process for Multiple Records in an Analysis Window

In general, if multiple, valid, non-missing observations exist at a visit or collection time point then records will be chosen based on the following:

- The record closest to the nominal time point in question, or,
- The later record if the two visits are equidistant from the time point, or,
- The average (arithmetic mean) if there is more than one record at the time point (generally applies to assessments done in triplicate).

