9.3.6 Clinical Laboratory Results

The study used a mixture of local and central labs, lab units, normal ranges will be converted using the Standard International lab unit if possible. Lab data will be counted as Low, Normal, and High for each visit by applying the local lab normal ranges. Lab shift tables from baseline to discharge/follow-up will be summarized.

Clinical laboratory test results will be listed by subject. Reference ranges provided by the laboratory for each parameter will be used to evaluate the clinical significance of laboratory test results. Values falling outside of the relevant reference range will be flagged, as appropriate, in the data listings. Abnormalities in clinical laboratory test results will be listed in a separate listing.

Cumulative urine volume over the 24-hour period for each dosing day will be summarized by Study Day and dose.

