Figure 15.2.16.2	Individual Plots in 24 Hours Vital Signs Monitor - Diastolic Blood Pressure over Time
Figure 15.2.16.3	Individual Plots in 24 Hours Vital Signs Monitor - Heart Rate over Time
Figure 15.2.16.4	Individual Plots in 24 Hours Vital Signs Monitor - Mean Arterial Pressure over Time
Figure 15.2.17.1	Individual Change from Baseline in Vital Signs - Change from Supine SBP to Seated SBP over Time
Figure 15.2.17.2	Mean +/ SD Change from Baseline in Vital Signs - Change from Supine SBP to Seated SBP over Time
Figure 15.2.17.3	Mean +/ SD Change from Baseline in Vital Signs - Change from Supine SBP to Seated SBP over Time by Subgroups
Figure 15.2.17.4	Individual Actual Value in Vital Signs - Change from Supine SBP to Seated SBP over Time for All Subjects and Part C Completers
Figure 15.2.17.5	Mean +/ SD Actual Value in Vital Signs - Change from Supine SBP to Seated SBP over Time
14.3	Safety
14.3.1	Extent of Exposure
14.3.1.1	Study Drug compliance
14.3.1.2	Summary of Exposure by Visit
14.3.1.3	Number (%) of Subjects with Exposure by Visit
13.3.2	Overview of adverse events
14.3.3.1	Treatment-emergent adverse events by system organ class and preferred term

14.3.3.2	Treatment-emergent adverse events by preferred term
14.3.4	Treatment-emergent adverse events occurring in >2% subjects by preferred term and sorted by decreasing frequency
14.3.5	Treatment-emergent adverse events by system organ Class, preferred term, and maximum severity
14.3.6	Treatment-emergent adverse events by system organ Class, preferred term, and Treatment Relationship
14.3.7	Study drug related treatment emergent adverse events by system organ class and preferred term
14.3.8.1	Serious adverse events by preferred term
14.3.8.2	Serious adverse events by system organ class and preferred term
14.3.10.1	Shift Table of Laboratory values from baseline to Worst Increase by laboratory test group, lab parameters
14.3.10.2	Shift Table of Laboratory values from baseline to Worst Decrease by laboratory test group, lab parameters
14.3.11.1	Summary of vital signs and Change from baseline by parameter and visit
14.3.11.2	Number (%) of patients with potentially clinically significant Changes in vital signs by visit
14.3.12.1	Summary of ECG and Change from Baseline by parameters and visit
14.3.12.2	Number (%) of patients with abnormal ECG and Changes by categories by parameters and visit
Figure 14.3.1	Individual Change of Exposure over Time - All Subjects

Listings

Number	Title

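### The worst-increase and worst-decrease laboratory shift tables for Part C have no scheduled on-drug value to draw on, and the SAP's visit rules keep out some or all for-cause on-drug results.

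*SAP*

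**What the plan says.** **Tables.** Appendix 2 of the SAP lists two laboratory summary tables for Part C: 14.3.10.1, "Shift Table of Laboratory values from baseline to Worst Increase by laboratory test group, lab parameters", and 14.3.10.2, its worst-decrease counterpart. No other laboratory table appears in that list.

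**Text on laboratory shifts.** SAP 9.3.6 describes something else: "Lab shift tables from baseline to discharge/follow-up will be summarized". It does not define worst.

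**Which records count.** SAP 6.1 says that, unless noted otherwise, "only data from scheduled visits will be included in the summaries, statistical analysis, and calculation of derived parameters". SAP 6.3 closes its visit rule with "Data collected at the unscheduled visit will not be counted in the summary table, however will be included in the subject listings". The same section also says: "The terminology of unscheduled will be applied to assessments that are outside an analysis window regardless, of the nominal label associated with the assessments". The laboratory rules in 6.4 cover a missing baseline, retests of invalidated specimens and values below the limit of detection. They do not mention unscheduled results.

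**When labs are drawn.** In Protocol Table 2 the row "Safety labs: Hematology, Chemistry, and UA" is marked at Day -2 and Day 169 only. Footnote o adds "Safety labs should be collected Day -2 or on Day -1". Footnote m puts the last dose on Day 140. Protocol 6.2 foresees extra draws: "Additional safety laboratory tests may be drawn as needed to manage any emergent health needs as directed by the Investigator". Protocol 6.1 also allows added laboratory safety tests during the study.

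**The concern.** A worst-value shift table exists to catch the most extreme result a subject had while exposed, including a transient one. Here the schedule supplies no on-drug laboratory value. The only on-drug values that can exist are extra draws, many of them made because something had gone wrong, and the SAP's general visit rule keeps such draws out of summary tables.

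At stake is how the tabulated laboratory summary reads. A reader who sees worst in the title will assume that on-treatment results were searched. If nearly every subject contributes one value taken about four weeks off drug, a table with few shifts says little about laboratory effects of TD-9855 during dosing. Part C has no concurrent control and the study has no data monitoring committee, so the summary tables carry more of the descriptive safety account than they otherwise would.

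**Working it through.** There is no planned figure to reproduce. The check counts scheduled values and then applies the inclusion rules.

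**1. Scheduled labs in Part C (Protocol Table 2).** The safety-lab row has 14 study-day columns and 2 marks: Day -2 (or Day -1 by footnote o) and Day 169. As a check on column alignment, the ECG row gives Day -1 and Day 169, and the Day -1 mark agrees with the ECG baseline in SAP 6.2.
- Scheduled post-baseline values per subject: 1.
- Scheduled values on dosing Days 1 to 140: 0.

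**2. Distance of that value from treatment.**
- Nominal: 169 - 140 = 29 days after the last dose.
- Extremes of the SAP 6.3 windows (133 to 147 and 163 to 175): 163 - 147 = 16 days, and 175 - 133 = 42 days.

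**3. Consequence for the two tables.** With one eligible post-baseline value, the highest and the lowest are the same number, so both tables are built from the same observation.

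**4. Unscheduled on-drug labs: two readings of SAP 6.3.**
- *Strict reading.* The closing sentence of 6.3, with 6.1, excludes data from unscheduled visits wherever they fall. Eligible dosing days: 0 of 140.
- *Permissive reading.* Only results outside an analysis window are unscheduled, whatever their label in the database. Dosing days inside a window: Days 5-32 (28), 50-64 (15), 78-92 (15), 106-120 (15) and 133-140 (8), so 28 + 45 + 8 = 81.
- Dosing days outside every window: 140 - 81 = 59. These are Days 1-4 (4), 33-49 (17), 65-77 (13), 93-105 (13) and 121-132 (12), and 4 + 17 + 13 + 13 + 12 = 59.

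For-cause results are thus excluded on 59 days under either reading, and on all 140 under the strict one.

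**5. Illustration (hypothetical).** ALT is normal at baseline, high on an extra draw on Day 40 and normal on Day 169. Day 40 lies in the gap 33-49, so both tables show normal to normal under either reading. The same rise on Day 29 would enter under the permissive reading and not under the strict one.

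**6. Early discontinuation.** The protocol synopsis places follow-up visits 2 and 4 weeks after the final dose. Assume the end-of-study lab is drawn exactly 28 days after a last dose on Day d, for d = 1 to 139, so that it falls on Days 29 to 167.
- In any SAP window: Days 29-32 (4), 50-64 (15), 78-92 (15), 106-120 (15), 133-147 (15), 148-162 (15) and 163-167 (5), which sum to 84 of 139.
- In the Day 169 window: 5 of 139.

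For the other 139 - 84 = 55 possible last-dose days the lab lies outside every window. Applied literally, the rule leaves such a subject with no post-baseline laboratory value in the tables unless another eligible draw exists.

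**The case against.** The tempting stronger reading is that no on-drug laboratory result can ever reach these tables, and that laboratory toxicity would therefore go unreported. The documents do not support either half.

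- **The exclusion is not certain on every day.** The window wording in 6.3 ties unscheduled to lying outside a window, which could admit an extra draw on 81 dosing days. This stands as a real ambiguity. It does not rescue the plan: the closing sentence of 6.3 points the other way, and two programmers could build different tables from the same text.
- **The count of one value rests on one protocol version.** SAP section 3 describes a separate Part C regimen for subjects enrolled under Amendment 2, whose laboratory schedule is not in the documents. This stands; the count cannot be asserted for everyone.
- **Four weeks off drug is not assured.** Protocol 6.4.1 asks, when possible, for termination-visit tests at withdrawal, so a final lab may come sooner. This also stands.
- **Abnormal results are reported elsewhere.** All data, scheduled or not, are listed; out-of-range values are flagged; SAP 9.3.6 adds a separate listing of abnormalities; and Protocol 7.5 has clinically significant findings recorded as adverse events, which enter the TEAE tables. This stands and confines the defect to the laboratory summary tables.
- **A table title is not a derivation.** SAP 6.1 allows exceptions, and 6.8 mentions a mock-shell document that may define worst. That document is not available here, and the word worst in a title does not say which records qualify.

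**Conclusion.** The point holds in limited form. Under the supplied protocol and the SAP as written, Tables 14.3.10.1 and 14.3.10.2 contain no scheduled on-drug value and usually rest on one shared off-drug value, nominally 29 days after the last dose. For-cause on-drug labs are excluded on at least 59 of 140 dosing days and possibly on all of them. SAP 9.3.6 and the Appendix 2 titles describe different tables and must be reconciled in any case.

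The conclusion assumes dosing through Day 140, the Table 2 schedule for all subjects, and no overriding rule in the unseen mock shells. A reader might infer that the plan hides laboratory toxicity. It does not: the listings and adverse-event tables remain. Nor does the SAP claim that the tables show an absence of toxicity; the analysis is descriptive throughout. The fault is that tables titled as worst-value summaries cannot, under the stated rules, reliably do that job.

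**What to change.** Add to SAP 9.3.6: Tables 14.3.10.1 and 14.3.10.2 use the highest and lowest result, relative to the reporting laboratory's reference range, among all results after the first Part C dose, scheduled and unscheduled, through the later of 30 days after the last dose or the subject's final follow-up or termination lab; the scheduled-visit and window limits in 6.1 and 6.3 do not apply to these tables.

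A plain 30-day cut-off would not do. After a Day 140 last dose it ends on Day 140 + 30 = 170, while the Day 169 window runs to Day 175, so a valid lab on Days 171-175 would be dropped. After a last dose on Day 133 it ends on Day 163.

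Keep the baseline-to-follow-up shift as a separate table, and footnote the number of subjects with at least one on-drug result.

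The cost is a short addition to the SAP and a small programming change, with no new samples or visits. The downside is that for-cause draws are selective, so the tables will look less favourable and need the footnote to be read fairly.
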